## INTRODUCTION

Ureteral stents are commonly-employed during routine stone procedures, including ureteroscopy, percutaneous nephrolithotomy, and shockwave lithotripsy. Their primary function is to preserve drainage and decompression of urine on the affected side. After stone procedures, they are commonly employed to counteract ureteral swelling which may otherwise temporarily impair drainage.

Though considered a staple of modern urology, ureteral stents are nonetheless the source of complaints from patients, who often report significant bother associated with the presence of a stent. Symptoms include urinary urgency and frequency from irritation of the bladder by the stent, pain in the back associated with reflux of urine along the stent, minor aches and cramping from the stent itself, blood in the urine, and discomfort during removal in the office. Over the past few decades, newer and smaller stents have become available; however, studies evaluating the impact of these newer stent technologies have been conflicting. Catheter/stent diameter is measured in French scale (Fr.). The french size is a measurement of external diameter of the catheter, not the internal drainage channel. (Fr. = D (mm) x 3) We plan to use 6Fr soft and hydrophobic, to prospectively evaluate the effect of stent composition upon patient comfort and satisfaction following stone surgery.

## RESEARCH QUESTIONS

Are hydrophobic stents more comfortable than standard soft stents?

## METHODS

### *Study design*

This is a single institution, randomized, single-blinded study to evaluate patient comfort and satisfaction following surgical stone management procedure with randomization allocation ratio of 1:1 (size 6Fr, soft; size 6Fr, hydrophobic;). Catheter diameter is measured in French scale (Fr.) the french size is a measurement of external diameter of the catheter, not the internal drainage channel. (Fr. = D (mm) x 3)

This study will be conducted at Washington University and will enroll 100 participants.

### *Subjects*

The study team will identify eligible patients from WU Urology patient population based on the following inclusion/exclusion criteria:

### *Inclusion Criteria*

The following patients will be eligible for participation in the study:

1. Over 18 years of age and willing and able to provide informed consent

2. Patients with current urinary stone disease, undergoing any procedure requiring a stent placement

### ***Exclusion Criteria***

The following patients will **not** be eligible for participation in the study:

1. Patients with compromised urinary tract due to cancer (e.g. bladder tumor, ureteral obstruction from non-GU malignancy)
2. Patients requiring bilateral surgical stone management procedure
3. Patients with any single stone exceeding 1.5 cm
4. Patients with severe concurrent disease, infection, or co-morbidity that, in the judgment of the investigator, would render the patient inappropriate for enrollment
5. Any patient who is on a genitourinary anticholinergic medication at baseline

### ***Study procedures***

#### **Screening and Informed Consent**

Subjects will be seen and counseled by their Urologist as part of the normal course of practice. Once a decision is made to proceed with a surgical procedure for stone management (cystoscopy with stent placement, ureteroscopy with intracorporeal lithotripsy), patients will be offered study participation and one of the members of the research team will discuss the study with them.

The discussion regarding study participation will take place in a private setting, such as in a private consult room, to maintain confidentiality. HRPO approved consent form will be used to guide the consent process and document participant's consent. During the consent process, the study team will explain that all stents used in this study are consistent with standard of care, but that an attempt is being made to determine features of the stent which may affect patient satisfaction. Patients will be asked to allow themselves to be randomized with respect to the stent they will receive. Patients will be encouraged to ask questions and discuss the study with family. They will be given ample time to review the consent. It is possible that some participants may be contacted by phone to assess their interest in this study. If the participant expresses interest in the study, informed consent form will be mailed/mailed to him/her. This will be done in an effort to allow the patient ample time to read the consent at home, consider the study and discuss it with friends and family. This will not replace the face to face consent discussion the research team will have with the patient prior to signing the consent form.

Patients may decline to participate without an impact on their care. They will not be pressured to participate. No study related procedures will take place prior to the completion of the informed consent process and participant signing the HRPO approved consent.

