#### Day 0 (Stent Insertion)

Randomization will take place prior to the procedure. Patients will be randomized in a 1:1 ratio for stent composition, soft vs. hydrophobic, for a total of 50 patients in each cohort. To minimize selection bias, a randomization table will be developed before initiation of enrollment. Envelopes containing randomization assignments will be created, sequentially numbered and sealed. Once enrollment is initiated, randomization envelopes will be opened for each subject after informed consent is granted and study eligibility is confirmed. Subjects will be blinded to the stent assignment so their reported pain level and satisfaction is not influenced by the knowledge of the inserted stent type.

The surgical procedure for stone management will be performed via an approach consistent with current standards-of-care.

Patients will be discharged on a standard regimen, consisting of Norco, or an equivalent narcotic, tamsulosin, and docusate. Patients will not be placed on anticholinergic or phenazopyridine medications at discharge.

When clinically indicated, exchange of stent is permitted. The patient data will be evaluable so long as adherence to initial randomization stratification is maintained.

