#### At the Time of Stent Removal

The participants will be asked to complete the following questionnaires prior to stent removal:

- Ureteric Stent Symptoms Questionnaire 1 with Analog Pain Scale included (USSQ 1 stent in situ)
- AUA Symptom Score Questionnaire
- Satisfaction Questionnaire

In addition, the patients will be asked to share with us the number of days pain pills have been taken, and their compliance with tamsulosin and docusate. We will assess for any use of anticholinergics, other analgesics and antibiotics.

The participants will then undergo cystoscopic removal of the stent in clinic.

Results of any standard of care imaging obtained prior to stent removal will be collected.

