## ***Covariate data***

1. Gender
2. Race

3. Height
4. Weight
5. Patient medical/surgical history
6. Type of procedure
7. Etiology of disease

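### Stent-only and ureteroscopy patients share one unstratified randomisation with no committed analysis by procedure, and the forms are not tied to a particular stent after an exchange or re-insertion

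*Combined protocol and SAP*

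**What the plan says.** **Who enters.** Under Screening and Informed Consent, two procedures are named as leading to an offer of participation: "surgical procedure for stone management (cystoscopy with stent placement, ureteroscopy with intracorporeal lithotripsy), patients will be offered study participation". The second inclusion criterion is at least as wide: "Patients with current urinary stone disease, undergoing any procedure requiring a stent placement". Neither requires that the stone be treated at the operation that places the stent.

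**Aim.** The Introduction plans to "prospectively evaluate the effect of stent composition upon patient comfort and satisfaction following stone surgery". The Research Questions section asks more broadly: "Are hydrophobic stents more comfortable than standard soft stents". Study design refers to comfort and satisfaction after a surgical stone management procedure.

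**Randomisation and analysis.** The Day 0 section says: "Patients will be randomized in a 1:1 ratio for stent composition, soft vs. hydrophobic, for a total of 50 patients in each cohort". It later speaks of keeping to the initial stratification of the randomisation, but no strata are defined anywhere. Covariate data lists "Type of procedure". Planned Statistical Analysis lists t-test, U-test, ANOVA, chi-squared and multivariate methods, with no model and no adjustment or subgroup by procedure.

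**Which stent the forms describe.** USSQ 1 is completed before stent removal, and then: "The participants will then undergo cystoscopic removal of the stent in clinic". USSQ 2, the post-stent form, follows 7 days after removal (±1 day in Table 1). The Day 0 section also states: "When clinically indicated, exchange of stent is permitted". Outcome measures lists the need for re-insertion among stent complications. No section says which stent USSQ 1 refers to, or which removal starts Day 7, when a participant has had more than one stent.

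**The concern.** Stent placement alone and stent placement at ureteroscopy with lithotripsy may produce different pain levels whichever stent is used. If so, an unstratified, unadjusted comparison carries procedure-to-procedure variation as noise, and the arms can differ by chance in procedure mix. Planned procedure is known before the envelope is opened and procedure type is already collected, so this noise can be removed at almost no cost. The variance estimate also feeds the second power analysis planned after 100 patients, which decides whether 100 more are enrolled.

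The second issue is what the forms measure. Where a stent has been exchanged or re-inserted, two coordinators could both follow the protocol and yet complete USSQ 1 for different stents, or count Day 7 from different removals. A form meant to describe the stent-free state could then be completed with a stent in place, and nothing in the data collection would show it.

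**Working it through.** **The plan's own figures first.** Power Analyses reports 216,000 simulations: 3 sample sizes × 3 SDs × 24 differences × 1000 = 216,000, which reproduces. It suggests that 100 patients may be ample for a difference above 3. With 50 per arm, two-sided alpha 0.05 and a normal approximation, power for a difference of 3 is above 99.9% at SD 1, 99.9% at SD 3 and 85.1% at SD 5, in line with that statement.

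**Inputs.**
- From the documents: 50 per arm; alpha 0.05 two-sided; SD values 1, 3 and 5.
- Assumed, because the documents give neither: stent-only share p of 10% to 40%; mean pain difference between procedures d = 2 points.
- Also assumed: the plan's SD values are used as within-procedure SDs. The plan calls them population SDs, which would already include any mixing.

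**Extra variance from pooling.** Added variance = p(1−p)d².
- p = 0.10: 0.10 × 0.90 × 4 = 0.36.
- p = 0.40: 0.40 × 0.60 × 4 = 0.96.

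Inflation = 1 + p(1−p)d²/SD². Half-width of the 95% interval for the arm difference = 1.96 × total SD × √(2/50) = 1.96 × total SD × 0.2.

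| Within-procedure SD | Variance inflation, p = 10% to 40% | Half-width with no procedure effect | Half-width when pooled |
|---|---|---|---|
| 1 | 1.36 to 1.96 | 0.39 | 0.46 to 0.55 |
| 3 | 1.04 to 1.11 | 1.18 | 1.20 to 1.24 |
| 5 | 1.014 to 1.038 | 1.96 | 1.97 to 2.00 |

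**Power, same assumptions.**
- SD 3, difference 2: from 91.5% to 90.5% (p = 10%) or 88.7% (p = 40%).
- SD 5, difference 3: from 85.1% to 84.6% or 83.8%.
- SD 1, difference 3: above 99.9% throughout.

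With a wider range (p of 10-50%, d of 1-3), power at SD 3 and difference 2 falls to 84.6% at worst, a loss of about 7 points.

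**Chance imbalance.** SE of the difference in stent-only share = √(p(1−p) × 2/50): 0.060 at p = 10% and 0.098 at p = 40%. The 95% range is ±12 to ±19 percentage points. Multiplied by d = 2, this shifts the arm difference by ±0.24 to ±0.38 points.

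**These are one quantity.** At SD 3 and p = 40%, √(1.18² + 0.38²) = 1.24, which is the pooled half-width in the table. The imbalance is already in the unstratified standard error and must not be counted again.

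**Forms.** No arithmetic applies. The removal section describes one removal in clinic followed by Day 7. The Day 0 section and the complications list both foresee a second stent. Nothing links the two.

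**The case against.** **Stent-only patients are within scope.** A reader might infer that they fall outside the objective because the Introduction speaks of comfort following stone surgery. The documents do not support that. The consent section itself classes cystoscopy with stent placement as a surgical procedure for stone management, Study design uses that same term, and the research question is not limited to any procedure. There is at most a tension in wording.

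**Day 7 contamination is not established.** A reader might also infer that stent-only patients keep their stone, return for a second operation and complete the Day 7 form with a new stent in place. No such pathway is described, and the removal section has stents taken out in clinic. A stent in place at Day 7 is a possibility that the plan leaves open, not an event that it states.

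**The plan may already cope.** Procedure type, baseline pain, imaging and residual stone burden are collected, and multivariate methods are mentioned. This stands in part: the data will exist. What is missing is a stated commitment on how procedure type enters the primary comparison. The primary pain score also has no stated time point, so the harm cannot be tied specifically to an in-situ score.

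**The loss is small.** This stands at SD 3 and SD 5. The large inflation at SD 1 needs a procedure effect of two within-procedure SDs, and power for a difference of 3 is not threatened there. If the plan's SDs are read as total SDs, its power figures already contain the mixing, and adjustment would simply be a gain.

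**Simple unstratified randomisation is legitimate.** Agreed: it is valid. The case for stratifying and adjusting is that both are nearly free.

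**Conclusion.** The point holds as a matter of precision and definition, not of bias or validity. Two procedure types share one randomisation with no defined strata, and no analysis by procedure is committed to. At SD 3 to 5 the avoidable variance is about 1% to 11%, or at most about 3 power points in the cases shown for a 10-40% share. It becomes large (36-96%) only at SD 1. All of this rests on the assumed stent-only share and the assumed 2-point procedure difference, neither of which is in the documents.

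The gap over which stent and which removal the forms refer to is real on the text alone, because the protocol permits exchange and lists re-insertion. Its size cannot be given: the documents do not say how often either is expected.

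**What to change.** **1. Randomisation and primary analysis.**
- In Day 0 (Stent Insertion), keep two sequentially numbered envelope series by planned procedure: stent placement alone, and stent placed at stone treatment. If enrolment has started, leave the randomisation as it is and rely on adjustment. Define the strata, or remove the reference to stratification.
- In Planned Statistical Analysis, include planned procedure type as a factor in the primary pain comparison, in all randomised patients. Use the planned procedure because it is fixed before randomisation.
- Give procedure-specific estimates as secondary results. Making the stone-treated group the main result would be costly: at a 40% stent-only share about 30 per arm remain, and t-test power for a difference of 3 at SD 5 falls from about 84% to 63%.

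**2. Forms.**
- Reconcile the Day 0, stent removal, Day 7 and Outcome measures sections, so that they state which stent USSQ 1 describes and which removal starts Day 7 after an exchange or re-insertion.
- Record whether any stent is in place when USSQ 2 is completed, and report the count by arm.
- Show the Day 7 comparison with and without those participants. Simply dropping them would be an exclusion on a post-randomisation event that may depend on arm or symptoms.

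**Cost.** A second envelope series, one model factor, one recorded item and one sensitivity analysis. No extra patients or procedures.

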#### **Baseline**

Once informed consent for study participation is obtained, patients will be asked to complete:

- AUA Symptom Score Questionnaire
- Analog pain scale

#### Day 0 (Stent Insertion)

Randomization will take place prior to the procedure. Patients will be randomized in a 1:1 ratio for stent composition, soft vs. hydrophobic, for a total of 50 patients in each cohort. To minimize selection bias, a randomization table will be developed before initiation of enrollment. Envelopes containing randomization assignments will be created, sequentially numbered and sealed. Once enrollment is initiated, randomization envelopes will be opened for each subject after informed consent is granted and study eligibility is confirmed. Subjects will be blinded to the stent assignment so their reported pain level and satisfaction is not influenced by the knowledge of the inserted stent type.

The surgical procedure for stone management will be performed via an approach consistent with current standards-of-care.

Patients will be discharged on a standard regimen, consisting of Norco, or an equivalent narcotic, tamsulosin, and docusate. Patients will not be placed on anticholinergic or phenazopyridine medications at discharge.

When clinically indicated, exchange of stent is permitted. The patient data will be evaluable so long as adherence to initial randomization stratification is maintained.

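### Allocation envelopes are opened before the procedure rather than once placement of a study stent is confirmed, and no rule covers a randomized patient who does not receive the assigned stent.

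*Combined protocol and SAP*

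**What the plan says.** The Day 0 (Stent Insertion) section of the combined protocol and SAP fixes the timing: "Randomization will take place prior to the procedure". The trigger is that "randomization envelopes will be opened for each subject after informed consent is granted and study eligibility is confirmed". Table 1 places both the second eligibility check and randomization on Day 0.

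The need for a stent enters through eligibility. Inclusion criterion 2 admits "Patients with current urinary stone disease, undergoing any procedure requiring a stent placement". The Screening and Informed Consent section names the procedures as "cystoscopy with stent placement, ureteroscopy with intracorporeal lithotripsy". The first includes stent placement by name; the second does not.

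On blinding, the Study design section says "This is a single institution, randomized, single-blinded study", and the Day 0 section says "Subjects will be blinded to the stent assignment so their reported pain level and satisfaction is not influenced". Neither says who opens the envelope, at what moment on Day 0, or when the surgeon learns the arm.

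The only statement on evaluability comes directly after the sentence allowing a stent to be exchanged: "The patient data will be evaluable so long as adherence to initial randomization stratification is maintained". No stratification factor is described anywhere, so I read this as adherence to the assigned stent type.

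**The concern.** Whether a stent is placed, and whether it is the assigned one, is settled during the procedure. Under the stated order the allocation is already revealed by then. Two things follow.

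First, a patient can be randomized and then leave without the assigned stent. If no stent was placed, USSQ 1, which is completed with the stent in place just before removal, cannot be obtained. The plan has no analysis set, no intention-to-treat statement and no allowance for losses that would settle what happens to that patient.

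Second, nothing in the plan keeps the arm from the surgeon while the decision to stent is still open. Numbered sealed envelopes protect enrolment. They do not protect a selection point that comes after opening. Patient blinding protects how pain is reported, not who remains in the comparison. If knowledge of the arm affects who stays in, the balance from randomization is lost for that part of the sample, and a larger sample does not restore it.

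**Working it through.** **Inputs from the documents.** 50 patients per arm (Day 0 section); two-sided alpha 0.05, SD scenarios 1, 3 and 5, and 24 differences from 0.1 to 4.7 (Power Analyses). No target difference or power is chosen, but a true difference above 3 is described as possibly sufficient with 100 patients, so I use 3.

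**Assumed inputs.** The documents give no rate of randomized patients who miss the assigned stent. I take 5% and 10%, equal in both arms, and 15% as an outer value. For selective loss I take 8% of one arm.

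**The plan's own figures.** 3 sample sizes x 3 SDs x 24 differences x 1,000 runs = 216,000, as stated. 2 x 50 = 100, as stated.

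**Power without losses.** Two-sample t-test, noncentrality = difference / (SD x sqrt(2/n)), df = 2n - 2.

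- SD 5: 3 / (5 x sqrt(2/50)) = 3 / 1.0 = 3.0; power 84.4%.
- SD 3: 3 / (3 x sqrt(2/50)) = 3 / 0.6 = 5.0; power 99.9%.

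This agrees with the plan's remark that 100 patients may be enough at a difference of this size.

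**Power with equal losses, difference 3.**

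| Assumed loss | Evaluable per arm | Power, SD 5 |
|---|---|---|
| 0% | 50 | 84.4% |
| 5% | 50 x 0.95 = 47.5 | 82.5% (82.1% at 47) |
| 10% | 50 x 0.90 = 45 | 80.4% |
| 15% | 50 x 0.85 = 42.5 | 78.1% |

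At SD 3 and 45 per arm, power is still 99.7%.

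**Randomizations needed to keep 50 evaluable per arm.** At 5%: 50 / 0.95 = 52.6, so 53 per arm, 106 in all. At 10%: 50 / 0.90 = 55.6, so 56 per arm, 112 in all.

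**Selective loss.** Let the full-arm mean be m, and let 8% of that arm, scoring m + 3, be dropped. The retained mean is (m - 0.08 x (m + 3)) / 0.92 = m - 0.24 / 0.92 = m - 0.26. With SD 5 and 50 per arm, the standard error of the difference is 5 x sqrt(2/50) = 1.0, so the shift is about a quarter of a standard error. With SD 3 it is 0.26 / 0.6 = 0.43 of one.

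**The case against.** Opening sequential sealed envelopes before a procedure, after consent and eligibility, is an accepted design. Eligibility already requires a procedure that needs a stent, one of the two named procedures is stent placement itself, and eligibility is checked again on the day of randomization. Losses may be few. The surgeon will learn the arm at placement in any case, both stents are described as standard of care, and pain is reported by blinded patients. The power cost is modest under the least favourable SD and negligible at SD 3.

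Most of this stands, and it limits the size of the point. It does not remove it: the stent requirement is judged before surgery, ureteroscopy is listed without stent placement, and nothing confirms placement before the arm is revealed.

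Three stronger readings are tempting, and the documents support none of them:

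- A reader might infer that the plan declares unstented patients non-evaluable. The evaluability sentence follows the exchange sentence and is most naturally about exchange. On unstented patients the plan is silent.
- A reader might infer that the surgeon is known to operate with knowledge of the arm. The plan permits this by silence but does not state it.
- A reader might infer that early opening demonstrably costs 5-10% of the sample. That range is assumed, as is the 8% selective loss.

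**Conclusion.** The point holds as an inexpensive improvement to the allocation procedure together with a gap in the analysis rules. It does not show that the trial is biased. Allocation is revealed before placement of a study stent is certain. Patients who then miss the assigned stent are covered by no rule, and the one evaluability sentence, written for exchange, depends on adherence to the assignment.

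The power cost at a difference of 3 and SD 5 is about 2 points at an assumed 5% loss and 4 points at 10% (84.4 - 80.4). Power drops below 80% only at the 15% loss, and the cost hardly registers at SD 3. The illustrative bias of 0.26 points is small against the sampling error, but unlike that error it does not shrink as patients are added. All of these sizes rest on assumed loss rates, and the two power costs also on equal loss in both arms.

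**What to change.** In the Day 0 section, replace the timing rule with wording such as: 'The next envelope in sequence is opened by a research team member in the procedure room once the surgeon has confirmed that a study stent will be placed, immediately before the stent is selected.' Move the randomization step to that moment in the operating procedures for the study. This changes when the arm is revealed, not any clinical decision about stenting.

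In Planned Statistical Analysis, add that every patient whose envelope is opened is analysed in the assigned arm, including after an exchange to the other stent type, and bring the evaluability sentence into line with this. State also how a missing stent-in-situ score is handled for anyone who is allocated but not stented, since keeping such a patient in the arm does not by itself supply a value.

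The cost is protocol wording, having both stent types and the envelope in the room, and a team member present to open it; the documents do not describe operating-room staffing, so that last item needs confirming. No visit is added. The change does not blind the surgeon, who still learns the arm at placement. It protects the decision to stent and the steps before it.

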## ***Outcome measures***

1. Stent
  - a. Type
  - b. Composition (soft or hydrophobic)
  - c. Length
2. Stent complications
  - a. Migration
  - b. Malposition
  - c. Dislodgement
  - d. Need for re-insertion
3. Time to stent removal
  - a. Clinically planned or required due to symptoms
4. Health Related Quality of Life
  - a. Ureteric Stent symptoms Questionnaire 1 and 2
  - b. AUA Symptom
5. Pain Score as reported by the participants on the self-administered assessment
6. Procedure Satisfaction Questionnaire
7. Use of analgesics for pain control
  - a. documented pain prescription at the time of discharge
  - b. self-reported duration of analgesics use after stent insertion (in days)
8. Residual stone burden
  - a. KUB, U/S, CT

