#### **Power Analyses**

Power is the probability to detect statistically significant results from a sample, if one actually exists in the population. In order to determine the sample size needed for adequate power, we are using an alpha (criterion of significance) of 0.05 in a two-tailed (non-directional) test (Figure) as our primary outcome is the pain index score.

Since there isn't a pilot study or previous work to base the assumptions of the power analysis, 216,000 simulations were performed varying sample size ( $n=100,150,200$ ), standard deviation of the population ( $\sigma=1,3,5$ ), and assumed true difference in population means of the pain index score (24 differences ranging from 0.1 to 4.7). For each combination of sample size, population standard deviation, and difference in population mean, 1000 simulations were tested. The results for these simulations are displayed graphically in Figure 1. The power analysis was calculated for soft versus hydrophobic stents.

Because of the uncertainty of the assumptions of the power analysis, it is recommended to perform an interim analysis at  $N=100$ . If there is low variability in the populations or if the true difference of the population is greater than 3 (or some combination of the two), 100 samples would potentially provide ample power to detect the differences in the populations.

Figure 1.

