### Planned Statistical Analysis

We will evaluate parameters, including stent composition, and outcomes including complications, hematuria, pain medication requirements, return to work/normal activities, subjective assessments of pain, discomfort and satisfaction, and factors associated with stent removal, including periprocedural discomfort, and need for early/delayed removal of the stent. We will use t-test, U-test, ANOVA, chi-squared tests, and multivariate statistical methods to evaluate our outcomes.

After 100 patients are accrued, an interim analysis will be performed in order to determine if the research questions are statistically significant at the 0.05 level. If they are significant results, patient enrollment will end. If they are not significant, a second power analysis will be performed to determine if 100 more patients would provide reliable statistical power of achieving significant results. This power analysis will be much more informative as there would be actual estimates of the populations of interest. If it is determined that an additional 100 more patients would still be unlikely to yield statistically significant results, patient enrollment will end. If it is determined that an additional 100 patients would be likely to yield statistically significant results, an additional 100 patients will be enrolled into the study.

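### The only rule on whose data count appears to drop patients exchanged to the other stent type, and no as-randomised analysis is stated

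*Combined protocol and SAP*

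**What the plan says.** Under Day 0 (Stent Insertion), the assignment concerns one factor: "Patients will be randomized in a 1:1 ratio for stent composition, soft vs. hydrophobic". The same section then provides that "When clinically indicated, exchange of stent is permitted", and follows at once with "The patient data will be evaluable so long as adherence to initial randomization stratification is maintained". On masking it says only that "Subjects will be blinded to the stent assignment"; nothing is said about the operator or whoever chooses a replacement stent.

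The Power Analyses section states that "our primary outcome is the pain index score". Outcome measures lists stent complications, among them "Need for re-insertion", and records whether removal was planned or driven by symptoms. Under At the Time of Stent Removal, "The participants will be asked to complete the following questionnaires prior to stent removal"; there is no separate instruction for a stent that is removed and replaced.

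Planned Statistical Analysis names methods ("We will use t-test, U-test, ANOVA, chi-squared tests, and multivariate statistical methods to evaluate our outcomes") and an interim rule at 100 patients. It names no analysis population. No section states an intention-to-treat or as-randomised analysis, or says how non-evaluable patients are handled.

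**The concern.** The evaluability sentence is conditional. A patient exchanged to the same type meets the condition and stays in. A patient exchanged to the other type fails it and, by implication though not in so many words, drops out.

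That makes inclusion depend on an event after randomisation. The reasons for exchange are not defined, and because only subjects are stated to be blinded, the replacement can be chosen by someone who knows the assignment. If off-type exchange goes with higher pain, and happens more often or by a different route in one arm, the patients left in that arm look better than the arm really did. A real difference can shrink, or a false one can appear. The condition covers patient data in general, so complication counts could lose events too.

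With no analysis set defined, the choice could also be made after the data are seen, including at the 100-patient look that decides whether enrolment ends.

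**Working it through.** **Inputs from the plan.** 50 patients per arm (Day 0); two-sided alpha 0.05; SD 1, 3 or 5; differences 0.1 to 4.7 (Power Analyses). The stated simulation count reproduces: 3 × 3 × 24 × 1,000 = 216,000. The plan gives no power figure. A difference of 3 at SD 5 is 3/5 = 0.6 SD, and the two-sample t-test with 50 per arm then has 84% power, which fits the plan's qualitative statement about 100 patients.

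**Assumed, because the plan is silent.** Off-type exchange of 0% to 10% per arm; a correlation r of 0.5 or 0.8 between the tendency to be excluded and pain.

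**Bias with no true difference.** Removing the top share p on a normal latent variable with correlation r to pain shifts the retained mean by −r·φ(z)/(1 − p), with z the upper-p normal quantile.

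- p = 0.05: φ(1.645)/0.95 = 0.1031/0.95 = 0.1086; times 0.5 = 0.054 SD, times 0.8 = 0.087 SD.
- p = 0.10: φ(1.282)/0.90 = 0.1755/0.90 = 0.195; times 0.5 = 0.098 SD, times 0.8 = 0.156 SD.

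Rejection rates are from 40,000 simulated trials per scenario, 50 per arm, t-test:

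| Excluded, one arm vs other | Bias (SD), r = 0.5 / 0.8 | Rejection at the 5% level |
|---|---|---|
| 5% vs 0% | 0.054 / 0.087 | 5.9% / 7.3% |
| 10% vs 0% | 0.098 / 0.156 | 7.4% / 11.9% |
| 10% vs 5% | 0.044 / 0.068 | 5.5% / 6.5% |
| 10% vs 10% | 0 / 0 | 5.0% / 4.9% |
| any of these, r = 0 | 0 | 4.9% to 5.2% |

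The two rows with 0% in one arm correspond to 0.05 to 0.16 points at SD 1, 0.16 to 0.47 at SD 3 and 0.27 to 0.78 at SD 5.

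A different selection model, in which off-type exchange occurs only in the most painful third of each arm, gives the same picture: 10% vs 0% has a bias of 0.12 SD and rejection of 9.0% to 9.4%; equal rates give about 5%. Keeping everyone as randomised gives 4.7% to 5.1% throughout.

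**True difference of 0.6 SD, same pain threshold for exclusion in both arms.** The other arm's latent variable is lower by 0.6r, so fewer of its patients are excluded. Example, 5% excluded in the worse arm with r = 0.5: the other arm's cut-off is 1.645 + 0.3 = 1.945, so 2.6% are excluded, and the estimate is 0.6 − 0.054 + 0.031 = 0.577 SD.

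The as-randomised columns assume that a crossover patient's score takes the other stent's mean: 0.6 × (1 − 0.05 − 0.026) = 0.554 SD in the same example. The table gives the simulated values, which agree with the closed form to within 0.003 SD.

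| Worse / other arm off-type | r | Excluded: estimate, power | As randomised: estimate, power |
|---|---|---|---|
| 5% / 2.6% | 0.5 | 0.574, 81.3% | 0.556, 78.3% |
| 5% / 1.7% | 0.8 | 0.546, 79.3% | 0.562, 79.9% |
| 10% / 5.7% | 0.5 | 0.561, 78.6% | 0.506, 70.3% |
| 10% / 3.9% | 0.8 | 0.513, 75.0% | 0.518, 73.3% |

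If crossover occurs only in the worse arm, exclusion gives 0.44 to 0.55 SD with 61% to 77% power, and as-randomised analysis gives 0.54 to 0.57 SD with 78% to 82%.

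**The case against.** The exclusion is inferred. The sentence follows the permission to exchange and may have been meant as reassurance that an exchange does not cost the patient's data if the assigned type is used again. Read that way, it would also discourage crossover. This is a fair account of what the authors may have intended, but it leaves the off-type patient either non-evaluable or unaddressed, so the sentence needs rewriting on any reading.

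Materiality cannot be shown from the documents. A patient must need an exchange and then receive the other type, and neither rate is given. No section links exchange to pain; the symptom-driven item concerns time to removal. The 11.9% figure needs about 5 of 50 excluded in one arm, none in the other, and a correlation of 0.8. All of this stands as a limit on the size of the problem.

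As-randomised analysis is not always the more powerful choice. With crossover in both arms it has lower power than exclusion in three of the four scenarios and is about equal in the fourth, because a questionnaire completed after an exchange may describe the other stent. This stands too. The argument for it is validity: if the stents do not differ, the test stays at 5% whoever is exchanged and why.

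**Conclusion.** The concern holds. The plan's only rule on evaluable data implies dropping patients on an event after randomisation that may be related to the outcome, and nothing elsewhere restores the randomised comparison.

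How much this matters is unknown. On the assumed rates it ranges from no effect (exclusion unrelated to pain, or no true difference with the same rate and mechanism in both arms) to a false-positive rate of about 12%. With a true difference of 0.6 SD and one pain threshold for both arms, the estimate falls to between 0.51 and 0.58 SD and power from 84% to between 75% and 81%. If off-type exchange is rare, the effect is small. It should be fixed, because the fix is cheap and must be in place before the 100-patient analysis.

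**What to change.** Replace the evaluability sentence with text to this effect:

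> All randomised patients are analysed in the arm assigned, whatever stent is used at any exchange. Questionnaires continue to be collected after an exchange. Exchanges and re-insertions are reported by assigned arm, with reasons.

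Repeat the analysis set under Planned Statistical Analysis. State there which in-situ USSQ score is analysed for a patient who had an exchange, since the schedule ties it only to stent removal. Keep the adherent-only set as a named sensitivity analysis. The permission to exchange does not change.

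The cost is one or two sentences, with no extra patients or visits, since the questionnaires at removal and at day 7 are collected anyway. The price is some dilution when a score reflects the other stent: at a true 0.6 SD, power of 70% to 80% with crossover in both arms, or 78% to 82% with crossover in the worse arm only, against 84% with no crossover.
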